##### 10.6.8.1 Female Participants who Become Pregnant

The Investigator will collect pregnancy information on any female participant who becomes pregnant while participating in this study. Information will be recorded on the Pregnancy Reporting form and submitted to the Sponsor within 24 hours of learning of a participant's pregnancy.

Any female patient who becomes pregnant while participating in the study must immediately discontinue study drug.

##### 10.6.8.2 Male Patients with Female Partners who Become Pregnant

The Investigator will attempt to collect pregnancy information on any male patient's female partner who becomes pregnant while the male participant is in this study. This applies only to male patients who receive study drug.

After obtaining the necessary signed informed consent from the pregnant female partner directly, the Investigator will record pregnancy information on the appropriate form and submit it to the Sponsor within 24 hours of learning of the partner's pregnancy. The female partner will also be followed to determine the outcome of the pregnancy. Information on the status of the mother and child will be forwarded to the Sponsor.

## 11 SUMMARY OF CHANGES (SOC)

List of Minor/Administrative Changes:

- Table of Contents was updated to reflect changes in protocol.
- List of Tables and Figures was updated to reflect changes in protocol.
- Minor changes were made to correct inconsistencies, typographical and grammatical errors.
- Updated References

### Detailed Summary of Changes Version 2:

Changes made from Protocol v2.0	Rationale	Relevant Section(s)
Updated safety follow-up period to 90 days.	Per FDA request the safety follow up period has been extended to 90 days.	
 
- Changes made throughout
 
- Table 3: Schedule of Assessments
 

Added term IMP to list of abbreviations	The abbreviation IMP is used in the body of the protocol and was not included in the past list of abbreviations	
 
- List of Abbreviations
 

Updated IC #4a to include 'any' high-grade serous component	This is to clarify that any high-grade serous component is acceptable for IC #4a.	
 
- Synopsis – Inclusion Criteria
 
- Section 5.1 – Inclusion Criteria
 

Removed language "such patients must have recovered adequately from any side effects of such therapy"	This is an exclusion criterion so the language is not necessary.	
 
- Synopsis – Exclusion Criteria
 
- Section 5.2 – Exclusion Criteria
 

Updated pleural ascites drainage language	Removed (<1 drainage) language to be definitive	
 
- Synopsis – Exclusion Criteria
 
- Section 5.2 – Exclusion Criteria
 

Added TSH to SOC	Atezo single agent does not seem to affect thyroid functions vs combo therapy with atezo, where hypo/hyperthyroidism is more prevalent.	
 
- Schedule of Assessments
 

Removed language for no protocol waivers or exemptions	Removed: "Protocol waivers or exemptions to the inclusion and exclusion criteria are not permitted." as IC #6 allows discussion with Medical	
 
- Section 5: Study Population
 

Changes made from Protocol v2.0	Rationale	Relevant Section(s)
	Monitor.	
Added section 4.5 Safety Follow-up Period to body of protocol	This is included in the Synopsis but was previously not included in the body of the protocol.	- Section 4.5
Added Section 4.6 Response/Survival Follow-up Period	This is included in the Synopsis but was previously not included in the body of the protocol	- Section 4.6
Clarified disease progression SAE requirement	The previous language was not clear that progression of leading to death should be reported as an SAE.	- 8.3.2.2

## 13 APPENDICES

### Appendix 1: Response Evaluation Criteria in Solid Tumors Version 1.1 (RECIST 1.1) and Immune-related RECIST

Response and progression will be evaluated in this study using the international criteria proposed by the RECIST 1.1 and iRECIST.

Tumor evaluation must include thoracic, abdominal, and pelvic imaging. This anatomic coverage is appropriate for both baseline imaging and on-treatment imaging.

Contrast-enhanced computed tomography (CT) is the preferred method to measure lesions selected for response assessment. This protocol has defined measurability of lesions when CT slice thickness is 5 mm or less. Magnetic resonance imaging (MRI), typically with gadolinium-based intravenous (IV) contrast, is also acceptable in certain situations, positron emission tomography (PET)-CT scans may be used providing that the measures are obtained from the CT scan and the CT scan is of the same diagnostic quality to a diagnostic CT (with IV and oral contrast).

#### RECIST

Changes in only the largest diameter (unidimensional measurement) of the tumor lesions are used in the RECIST 1.1. Rules described in the following for CT are equally valid for MRI.

##### Measurable disease

*Tumor lesions:* Must be accurately measured in at least one dimension (longest diameter in the plane of measurement is to be recorded) with a minimum size of:

- 10 mm by CT scan
- 10 mm caliper measurement by clinical exam
- 20 mm by chest x-ray

Computed tomography is strongly recommended.

*Malignant lymph nodes:* To be considered pathologically enlarged and measurable, a lymph node must be  $\geq 15$  mm in short axis when assessed by CT scan (CT scan slice thickness recommended to be no greater than 5 mm). At baseline and in follow-up, only the short axis will be measured and followed. See also notes below on 'Baseline documentation of target and non-target lesions' for information on lymph node measurement.

##### Non-measurable disease

All other lesions, including small lesions (longest diameter  $< 10$  mm or pathological lymph nodes with  $\geq 10$  to  $< 15$  mm short axis) as well as truly non-measurable lesions. Lesions considered truly non-measurable include: leptomeningeal disease, ascites, pleural or pericardial effusion,

inflammatory breast disease, lymphangitic involvement of skin or lung. Bone lesions, cystic lesions, and lesions previously treated with local therapy require particular comment.

*Bone lesions:*

- Bone scan, PET scan, or plain films are not considered adequate imaging techniques to measure bone lesions.
- Lytic bone lesions, or mixed lytic-blastic lesions, with identifiable soft tissue components, that can be evaluated by cross sectional imaging techniques such as CT or MRI can be considered as measurable lesions if the soft tissue component meets the definition of measurability described above.
- Blastic bone lesions are non-measurable.

*Cystic lesions:*

- Lesions that meet radiographic criteria for simple cysts should not be considered malignant lesions (neither measurable nor non-measurable).
- “Cystic lesions” thought to be cystic metastases can be considered as measurable lesions, if they meet the definition of measurability. However, if non-cystic lesions are present in the same participants, these should be preferably selected for assessment.

Lesions with prior local treatment:

- Tumor lesions situated in a previously irradiated area, or in an area subjected to other loco-situated in a previously irradiated area, or in an area subjected to other loco-regional therapy, are usually not considered measurable unless there has been demonstrated progression in the lesion.

**Non-target lesions**

All other lesions (or sites of disease) including pathological lymph nodes (with short axis  $\geq 10$  mm and  $< 15$  mm) should be identified as non-target lesions and should also be recorded at baseline. Measurements are not required and these lesions should be followed as ‘present,’ ‘absent,’ or in rare cases ‘unequivocal progression’ (more details to follow). In addition, it is possible to record multiple non-target lesions involving the same organ as a single item on the Case Report Form (e.g., ‘multiple enlarged pelvic lymph nodes’ or ‘multiple liver metastases’).

**Response Criteria:** The BOR is the best response recorded from the start of the study treatment until the end of treatment. The subject’s BOR assignment will depend on the findings of both target and non-target disease and will also take into consideration the appearance of new lesions.

**Complete Response (CR):** Disappearance of all target lesions. Any pathological lymph nodes (whether target or non-target) must have decreased in size to have a short axis of  $< 10$  mm.

**Partial Response (PR):** At least a 30% decrease in the sum of diameters of target lesions taking as reference the baseline sum diameters.

**Stable Disease (SD):** Neither sufficient shrinkage to qualify for PR nor sufficient increase to qualify for progressive disease (PD), taking as reference the smallest sum diameters while on study.

**Non-CR/Non-PD:** Persistence of one or more non-target lesion(s) and/or maintenance of tumor marker level above the normal limits.

**Progressive Disease (PD):** At least a 20% increase in the sum of diameters of target lesions, taking as reference the smallest sum on study (this includes the baseline sum if that is the smallest on study). In addition to the relative increase of 20%, the sum must also demonstrate an absolute increase of at least 5 mm. For non-target lesions, unequivocal progression (see comments below) of existing lesions represents PD. Note: the appearance of one or more new lesions is also considered progression.

Lymph nodes identified as target lesions should always have the actual short axis measurement recorded (measured in the same anatomical plane as the baseline examination), even if the nodes regress to below 10 mm on study. This means that when lymph nodes are included as target lesions, the 'sum' of lesions may not be zero even if CR criteria are met, since a normal lymph node is defined as having a short axis of <10 mm.

To achieve unequivocal progression in participants with measurable disease on the basis of the non-target disease, there must be an overall level of substantial worsening in non-target disease such that, even in presence of SD or PR in target disease, the overall tumor burden has increased sufficiently to merit discontinuation of therapy. A modest 'increase' in the size of one or more non-target lesions is usually not sufficient to qualify for unequivocal.

In the absence of measurable disease, the same general concepts apply here as noted above.

### Target and Non-target Lesion Response

Target Lesions	Non-Target Lesions	New Lesions	Overall Response
CR	CR	No	CR
CR	Non-CR/Non-PD	No	PR
CR	Not evaluated	No	PR
PR	Non-PD or not all evaluated	No	PR
SD	Non-PD or not all evaluated	No	SD
Not all evaluated	Non-PD	No	NE
PD	Any	Yes or No	PD
Any	PD	Yes or No	PD
Any	Any	Yes	PD

Abbreviations: CR = complete response; NE = not evaluable; PD = progressive disease; PR = partial response; SD = stable disease.

Participants with a global deterioration of health status requiring discontinuation of treatment without objective evidence of disease progression at that time should be reported as "symptomatic deterioration."

Every effort should be made to document the objective progression even after discontinuation of treatment.

### Response duration

The duration of OS is measured from the time measurement criteria are initially met for CR/PR (whichever is initially recorded) until the initially date that recurrent or PD is objectively documented (taking as reference for PD the smallest measurements recorded on study).

The duration of overall CR is measured from the time measurement criteria are initially met for CR until the initially date that recurrent disease is objectively documented.

### Stable disease (SD) duration

Stable disease is measured from the start of the treatment until the criteria for progression are met, taking as reference the smallest sum on study (if the baseline sum is the smallest, this is the reference for calculation of PD).

### **Methods of measurement**

The same method of assessment and the same technique should be used to characterize each identified and reported lesion at baseline and during follow-up. When lesions can be evaluated by both clinical exam and imaging, imaging evaluation should be undertaken since it is more objective.

CT/MRI - CT and MRI are the best currently available and reproducible methods to measure target lesions selected for response assessment. As a general rule, the minimum size of a measurable lesion at baseline should be no less than double the slice thickness and also have a minimum size of 10 mm which requires a slice thickness. An MRI is also acceptable in certain situations.

Ultrasound - Ultrasound is not useful in assessment of lesion size and should not be used as a method of measurement. Ultrasound examinations cannot be reproduced in their entirety for independent review at a later date and, because they are operator dependent, it cannot be guaranteed that the same technique and measurements will be taken from one assessment to the next. If new lesions are identified by ultrasound in the course of the study, confirmation by CT or MRI is advised. If there is concern about the radiation exposure at CT, MRI may be used instead of CT in selected instances.

Tumor markers: tumor markers alone cannot be used to assess objective tumor response. If markers are initially above the upper normal limit, however, they must normalize for a participant to be considered in CR.

When effusions are known to be a potential adverse effect of treatment (e.g., angiogenesis inhibitors), the cytological confirmation of the neoplastic origin of any effusion that appears or worsens during treatment can be considered if the measurable tumor has met criteria for response or SD in order to differentiate between response (or SD) and PD.

## iRECIST

iRECIST is based on RECIST 1.1 but adapted to account for the unique tumor response seen with immunotherapeutic drugs. iRECIST will be used by the Investigator to assess tumor response and progression and make treatment decisions. When clinically stable, participants should not be discontinued until progression is confirmed by the Investigator, working with local radiology. This allowance to continue treatment despite initial radiologic PD takes into account the observation that some participants can have a transient tumor flare in the first few months after the start of immunotherapy, and then experience subsequent disease response. This data will be captured in the clinical database.

### *Assessment at Screening and Prior to RECIST 1.1 Progression*

Until radiographic disease progression based on RECIST 1.1, there is no distinct iRECIST assessment.

### *Assessment and Decision at RECIST 1.1 Progression*

For participants who show evidence of radiological PD by RECIST 1.1 as determined by the Investigator, the Investigator will decide whether to continue a participant on study treatment until repeat imaging is obtained using iRECIST for participant management. This decision by the Investigator should be based on the participant's overall clinical condition.

Clinical stability is defined as the following:

- Absence of symptoms and signs indicating clinically significant progression of disease
- No decline in ECOG performance status
- No requirements for intensified management, including increased analgesia, radiation, or other palliative care

Any participant deemed **clinically unstable** should be discontinued from study treatment at site-assessed first radiologic evidence of PD and is not required to have repeat tumor imaging for confirmation of PD by iRECIST.

If the Investigator decides to continue treatment, the participant may continue to receive study treatment and the tumor assessment should be repeated 4 to 8 weeks later to confirm PD by iRECIST, per Investigator assessment.

Tumor flare may manifest as any factor causing radiographic progression per RECIST 1.1, including:

- Increase in the sum of diameters of target lesion(s) identified at baseline to  $\geq 20\%$  and  $\geq 5$  mm from nadir
  - Note: the iRECIST publication uses the terminology "sum of measurements", but "sum of diameters" will be used in this protocol, consistent with the original RECIST 1.1 terminology.

- Unequivocal progression of non-target lesion(s) identified at baseline
- Development of new lesion(s)

iRECIST defines new response categories, including iUPD (unconfirmed progressive disease) and iCPD (confirmed progressive disease). For purposes of iRECIST assessment, the first visit showing progression according to RECIST 1.1 will be assigned a visit (overall) response of iUPD, regardless of which factors caused the progression.

At this visit, target and non-target lesions identified at baseline by RECIST 1.1 will be assessed as usual.

New lesions will be classified as measurable or non-measurable, using the same size thresholds and rules as for baseline lesion assessment in RECIST 1.1. From measurable new lesions, up to 5 lesions total (up to 2 per organ), may be selected as New Lesions – Target. The sum of diameters of these lesions will be calculated and kept distinct from the sum of diameters for target lesions at baseline. All other new lesions will be followed qualitatively as New Lesions – Non-target.

#### *Assessment at the Confirmatory Imaging*

On the confirmatory imaging, the participant will be classified as progression confirmed (with an overall response of iCPD), or as showing persistent unconfirmed progression (with an overall response of iUPD), or as showing disease stability or response (iSD/iPR/iCR).

#### *Confirmation of Progression*

Progression is considered confirmed, and the overall response will be iCPD, if ANY of the following occurs:

- Any of the factors that were the basis for the initial iUPD show worsening
  - For target lesions, worsening is a further increase in the sum of diameters of  $\geq 5$  mm, compared to any prior iUPD time point
  - For non-target lesions, worsening is any significant growth in lesions overall, compared to a prior iUPD time point; this does not have to meet the “unequivocal” standard of RECIST 1.1
  - For new lesions, worsening is any of these:
    - An increase in the new lesion sum of diameters by  $\geq 5$  mm from a prior iUPD time point
    - Visible growth of new non-target lesions
    - The appearance of additional new lesions
- Any new factor appears that would have triggered PD by RECIST 1.1

#### *Persistent iUPD*

Progression is considered not confirmed, and the overall response remains iUPD, if:

- None of the progression-confirming factors identified above occurs AND
- The target lesion sum of diameters (initial target lesions) remains above the initial PD threshold (by RECIST 1.1)

Additional imaging for confirmation should be scheduled 4 to 8 weeks from the imaging on which iUPD is seen. This may correspond to the next visit in the original visit schedule. The assessment of the subsequent confirmation imaging proceeds in an identical manner, with possible outcomes of iCPD, iUPD, and iSD/iPR/iCR.

#### *Resolution of iUPD*

Progression is considered not confirmed, and the overall response becomes iSD/iPR/iCR, if:

- None of the progression-confirming factors identified above occurs, AND
- The target lesion sum of diameters (initial target lesions) is not above the initial PD threshold.

The response is classified as iSD or iPR (depending on the sum of diameters of the target lesions), or iCR if all lesions resolve.

In this case, the initial iUPD is considered to be pseudo-progression, and the level of suspicion for progression is “reset”. This means that the next visit that shows radiographic progression, whenever it occurs, is again classified as iUPD by iRECIST, and the confirmation process is repeated before a response of iCPD can be assigned.

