#### *Detection of Progression at Visits After Pseudo-progression Resolves*

After resolution of pseudo-progression (i.e., achievement of iSD/iPR/iCR), iUPD is indicated by any of the following events:

- Target lesions
  - Sum of diameters reaches the PD threshold ( $\geq 20\%$  and  $\geq 5$  mm increase from nadir) either for the first time, or after resolution of previous pseudo-progression. The nadir is always the smallest sum of diameters seen during the entire trial, either before or after an instance of pseudo-progression.

- Non-target lesions
  - If non-target lesions have never shown unequivocal progression, their doing so for the first time results in iUPD.
  - If non-target lesions have shown previous unequivocal progression, and this progression has not resolved, iUPD results from any significant further growth of non-target lesions, taken as a whole.
- New lesions
  - New lesions appear for the first time
  - Additional new lesions appear
  - Previously identified new target lesions show an increase of  $\geq 5$  mm in the new lesion sum of diameters, from the nadir value of that sum
  - Previously identified non-target lesions show any significant growth

If any of the events above occur, the overall response for that visit is iUPD, and the iUPD evaluation process (see Assessment at the Confirmatory Imaging above) is repeated. Progression must be confirmed before iCPD can occur.

[figure not shown]
The decision process is identical to the iUPD confirmation process for the initial PD, with one exception: if new lesions occurred at a prior instance of iUPD, and at the confirmatory imaging the burden of new lesions has increased from its smallest value (for new target lesions, the sum of diameters is  $\geq 5$  mm increased from its nadir), then iUPD cannot resolve to iSD or iPR. It will remain iUPD until either a decrease in the new lesion burden allows resolution to iSD or iPR, or until a confirmatory factor causes iCPD.

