## Comparison of RECIST 1.1 and iRECIST Criteria

	RECIST 1.1	iRECIST
Definitions of measurable and non-measurable disease; numbers and site of target disease	Measurable lesions are $\geq 10$ mm in diameter ( $\geq 15$ mm for nodal lesions); maximum of five lesions (two per organ); all other disease is considered non-target (must be $\geq 10$ mm in short axis for nodal disease)	No change from RECIST 1.1; however, new lesions are assessed as per RECIST 1.1 but are recorded separately on the case report form (but not included in the sum of lesions for target lesions identified at baseline)
Complete response, partial response, or stable disease	Cannot have met criteria for progression before complete response, partial response, or stable disease	Can have had iUPD (one or more instances), but not iCPD, before iCR, iPR, or iSD
Confirmation of complete response or partial response	Only required for non-randomised trials	As per RECIST 1.1
Confirmation of stable disease	Not required	As per RECIST 1.1
New lesions	Result in progression; recorded but not measured	Results in iUPD but iCPD is only assigned on the basis of this category if at next assessment additional new lesions appear or an increase in size of new lesions is seen ( $\geq 5$ mm for sum of new lesion target or any increase in new lesion non-target); the appearance of new lesions when none have previously been recorded, can also confirm iCPD
Independent blinded review and central collection of scans	Recommended in some circumstances —eg, in some trials with progression-based endpoints planned for marketing approval	Collection of scans (but not independent review) recommended for all trials
Confirmation of progression	Not required (unless equivocal)	Required
Consideration of clinical status	Not included in assessment	Clinical stability is considered when deciding whether treatment is continued after iUPD

"i" indicates immune responses assigned using iRECIST. RECIST=Response Evaluation Criteria in Solid Tumours. iUPD=unconfirmed progression. iCPD=confirmed progression. iCR=complete response. iPR=partial response. iSD=stable disease.

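### Appendix 1 cannot keep a patient at iUPD when the progression came only from new or non-target lesions that are still present and unchanged; the patient becomes iSD or iPR on the target sum, and an iPR counts in iORR

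*Protocol*

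**What the plan says.** **Start of iUPD.** Protocol Appendix 1 (Assessment and Decision at RECIST 1.1 Progression) states that "the first visit showing progression according to RECIST 1.1 will be assigned a visit (overall) response of iUPD, regardless of which factors caused the progression". The listed causes are growth of the target sum, unequivocal non-target progression and new lesions.

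**Confirmation.** iCPD at the next scan needs worsening. For new lesions this is a rise of at least 5 mm in their sum, visible growth of those followed qualitatively, or "The appearance of additional new lesions". For existing non-target disease, "For non-target lesions, worsening is any significant growth in lesions overall, compared to a prior iUPD time point". A fresh cause of progression also confirms.

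**Persistent iUPD.** No confirming factor occurs, and "The target lesion sum of diameters (initial target lesions) remains above the initial PD threshold (by RECIST 1.1".

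**Resolution.** The first condition is "None of the progression-confirming factors identified above occurs, AND" and the second is "The target lesion sum of diameters (initial target lesions) is not above the initial PD threshold". The choice between iSD and iPR then rests on the target sum. Only iCR requires every lesion to have gone.

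**Comparison table, new-lesion row.** "Results in iUPD but iCPD is only assigned on the basis of this category if at next assessment additional new lesions appear", or if the new lesions grow.

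**SAP.** Section 8.2 keeps the iBOR window open through iUPD, closing it at iCPD or when treatment ends if that is sooner. It counts every iBOR of iCR or iPR in iORR. Section 8.3 tabulates both with a Clopper-Pearson interval. Section 8 refers to the RECIST 1.1 and iRECIST guidelines, but the SAP does not restate how iUPD resolves or say whether Appendix 1 governs.

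**The concern.** iUPD can start from three kinds of lesion, but once worsening has been excluded it is lifted by looking at only one of them. A patient may have a new metastasis that neither grows nor shrinks, while the baseline target lesions are stable or smaller. By RECIST 1.1 that patient has progressed. Under Appendix 1 the next scan is labelled pseudo-progression and classed as iSD or iPR, although the lesion that caused the progression has not changed.

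This fits poorly with the new-lesion row of the comparison table, which gives new lesions two consequences, iUPD or iCPD, and no route by which an unchanged one ceases to count. What is at stake is an upward shift in iORR, a secondary endpoint, and in the iBOR distribution. With few responders, one such patient would be visible in the table.

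**Working it through.** The plan states no figure to reproduce. The check applies the Appendix 1 rules to a first iUPD caused solely by new or non-target lesions, with a target sum not above the progression threshold at that visit.

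*Step 1: can this patient be persistent iUPD?* Persistence needs the target sum to remain above the threshold. A sum that was never above it cannot remain above it. If it crosses the threshold for the first time at the confirmatory scan, that is a new cause of progression and gives iCPD. Persistent iUPD is therefore unreachable.

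*Step 2: the classes at the confirmatory scan.* The last column applies the rule proposed under the fix.

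| Confirming factor | Causal new or non-target lesions | Target sum | Appendix 1 | With the fix |
|---|---|---|---|---|
| Yes | Any | Any | iCPD | iCPD |
| No | Present, unchanged | SD range | iSD | iUPD |
| No | Present, unchanged | PR range | iPR | iUPD |
| No | Present, unchanged | CR | iPR | iUPD |
| No | Gone | SD range | iSD | iSD |
| No | Gone | PR range | iPR | iPR |
| No | Gone, all lesions resolved | CR | iCR | iCR |

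Under Appendix 1 the SD and PR rows are the same whether the causal lesions remain or have gone. Their presence matters only when the target lesions have disappeared, where it turns iCR into iPR.

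*Step 3: route into iORR.* The iBOR window is still open after iUPD, so the iPR counts. All of the following must hold for a responder to be added: iUPD from new or non-target lesions alone; no worsening and no regression; target sum down at least 30%; and no earlier iPR or iCR. If the target sum is in the SD range, iBOR moves from iUPD to iSD, and only if nothing better was recorded before.

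*Step 4: scale.* Inputs are up to 30 subjects per cohort (Protocol 4.1) and the 95% Clopper-Pearson interval (SAP 8.3). The lower limit is the 2.5% point of Beta(x, n−x+1); the upper limit is the 97.5% point of Beta(x+1, n−x). For x = 0 the lower limit is 0 and the upper is 1 − 0.025^(1/n).

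- One patient at N=30: 1/30 = 3.3 points.
- 0/30: upper limit 1 − 0.025^(1/30) = 11.6%, so 0% (0 to 11.6).
- 1/30: 3.3% (0.1 to 17.2).
- 2/30: 6.7% (0.8 to 22.1); 3/30: 10.0% (2.1 to 26.5).
- At N=15 one patient is 1/15 = 6.7 points: 0/15 is 0% (0 to 21.8) and 1/15 is 6.7% (0.2 to 31.9).

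These are illustrations. The documents do not say how many patients, if any, meet the Step 3 conditions.

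**The case against.** The strongest reply is that the rule is deliberate. Appendix 1 asks for disappearance of all lesions only for iCR, so iSD or iPR with residual disease is contemplated. The section on progression after pseudo-progression resolves describes patients already classed iSD, iPR or iCR whose non-target progression has not resolved. The comparison table allows iPR after iUPD. This reply has force, most of all for non-target lesions, which the new-lesion row does not cover. It does not settle how an unchanged new lesion should be handled, and the SAP does not tell a reader that an iPR may coexist with the lesion that caused progression.

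Four stronger readings are tempting, and the documents do not support them.

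- A reader might infer that new and non-target lesions are ignored altogether. They are not: growth, additional lesions or a fresh cause of progression gives iCPD. The gap is limited to lesions that are present and unchanged.
- A reader might infer that later episodes have a protection which the first lacks, because there "It will remain iUPD until either a decrease in the new lesion burden allows resolution to iSD or iPR". That exception applies only when new-lesion burden has increased from its smallest value, so it would not hold back an unchanged lesion either. At a first episode, a rise of at least 5 mm in the new-lesion sum already gives iCPD.
- A reader might infer that the main result is inflated. The primary endpoint is ORR by RECIST 1.1, where a new lesion is PD and SAP 8.1 closes the window at PD. SAP 8 does not report DOR, PFS or OS, so restarting the progression assessment changes no reported time-to-event result.
- A reader might infer that Appendix 1 misstates the published iRECIST criteria. That cannot be judged from these documents and is not claimed.

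It is also fair to object that SAP 4.1 shows Part 1 responses were already known, so a changed derivation is post hoc. That stands, and the fix allows for it.

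**Conclusion.** The point holds in this narrow form. After a first iUPD with no confirming factor, the target sum alone separates persistence from resolution. Unchanged new or non-target lesions that caused the iUPD therefore cannot keep the patient at iUPD, and an iPR reached this way enters iORR.

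The direction is upward for iORR and towards better categories for iBOR. The size is unknown; each patient affected is worth 3.3 points in a full cohort of 30. No hypothesis test is attached to iORR. This is a modest correction to a descriptive secondary endpoint.

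The conclusion assumes that Appendix 1 as written governs the iBOR derivation and that an iPR counts as observed, as SAP 8.2 reads. If the response confirmation mentioned in the comparison table were applied, the iPR would also have to be confirmed.

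**What to change.** **SAP 8.2.** State which iUPD rule governs iBOR, and derive it as follows. After iUPD, a visit is iCPD if any Appendix 1 confirming factor is present. Otherwise it stays iUPD if the target sum is still above the threshold, or if any new or non-target lesion that caused the iUPD remains without regression. It becomes iSD, iPR or iCR only when neither applies. The test should be regression, not full disappearance, because the later-episode rule in Appendix 1 lets a decrease in new-lesion burden permit resolution. Appendix 1 gives no size for that decrease, so the SAP should define it.

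**Reporting.** Because Part 1 responses were known when the SAP was written, also report iORR under the Appendix 1 wording and list every patient whose class differs.

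**Appendix 1.** Reconcile the persistent-iUPD, resolution and later-episode passages with the comparison table, including the later-episode clause on unresolved non-target progression. The change proposed here concerns endpoint derivation only. The same categories also steer imaging and treatment after iUPD; how those passages are reconciled is left to the sponsor.

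**Cost.** A few sentences, one extra derivation and one listing. Appendix 1 has new lesions recorded separately, so new data collection should not be needed, though it should be checked that shrinkage of lesions followed only qualitatively was captured. iORR may come out slightly lower.
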